### **3.2.2 Secondary Safety Endpoints**

The secondary safety endpoints of this study include:

- TEAEs and SAEs
- AESIs (see Section 3.2.3.2) and imAEs (see Section 3.2.3.3)
- ECG
- Vital signs including systolic blood pressure (SBP), diastolic blood pressure (DBP), pulse rate, temperature, and respiratory rate
- Laboratory data including clinical chemistry, haematology and urinalysis
- Physical Examination

### **3.2.3 Adverse Events**

Details of all AEs and SAEs will be collected for a patient from the signing of the informed consent form (ICF) up to 90 days after the last dose of durvalumab. If an event starts after this period and the Investigator considers that it is possible that it is due to a late onset toxicity to durvalumab, then it should be reported as an AE or SAE.

All AEs will be coded using the latest version of Medical Dictionary for Regulatory Activities (MedDRA) providing the System Organ Class (SOC) and Preferred Term (PT).

In addition, all AEs will also be graded according to the National Cancer Institute (NCI) Common Terminology Criteria for AEs (CTCAE Version 4.03) allocating grades from Grade 1 to Grade 4 which will be used for the reporting. The meaning of these categories are as follows:

- Grade 1: Mild AE
- Grade 2: Moderate AE
- Grade 3: Severe AE
- Grade 4: Life-threatening or disabling AE
- Grade 5: Death related to AE

Treatment-emergent adverse events (TEAEs) are AEs that start after the first dose of durvalumab or which start prior to the first dose of durvalumab but worsen following the first dose of durvalumab, and where the start date/date of worsening is also no later than 90 days after the last dose of durvalumab or the initiation of the first subsequent therapy following discontinuation of durvalumab (whichever occurs first). Any TEAE will be included in the AE summaries as detailed in Section 4.5.1.

Missing start and stop dates for AEs will be imputed using the rules described in Section 4.1.3.

#### **3.2.3.1 Treatment-Related Adverse Events**

A TRAE is any AE with a relatedness to durvalumab of possible or probable, or where the

relatedness is missing. When the relatedness of an AE is missing on the eCRF, all efforts will be taken to ensure that the Investigator assigns his/her assessment of relatedness prior to database lock. In the tables, listings and figures, the TRAEs are presented as “possibly related adverse events” as per the CRF and AZ standards.

If relatedness of an AE is missing at the DBL, as given in Section 4.1.2, the AE will be considered as related to durvalumab.

### **3.2.3.2 Adverse Events of Special Interest**

An AESI is defined as an AE of scientific and medical interest specific to durvalumab and may require close monitoring and rapid communication by the Investigator to the sponsor. An AESI can be either serious or non-serious. All AESIs will be programmatically derived.

An AstraZeneca medically qualified expert, after consultation with the Global Patient Safety Physician, has reviewed all AEs of interest and identified which PTs contribute to each AESI. A further review will take place prior to DBL to ensure any further terms not already included are captured within the categories. The final list of PTs for all AESIs will be completed before DBL and documented in the Study Master File.

### **3.2.3.3 Immune-Mediated Adverse Event**

An imAE is defined as an AESI that is associated with drug exposure and is consistent with an immune-mediated mechanism of action and where there is no clear alternate etiology. In general, imAEs will include AESIs that are managed using steroids, immunosuppressants and/or hormone replacement therapy.

This document comprises the specification for the analysis of the imAEs as identified by the investigator (as recorded in CRF Adverse Events (AE)).

Time to event analyses for imAEs will be performed for the following definitions:

- Time to first onset of imAE: Start date of first imAE episode – First dose date + 1
- Time to first onset of imAE of Grade 3 or 4: First date of imAE episode that had CTCAE Grade 3 or 4 – First dose date + 1
- Time to resolution of imAE: End date of imAE episode – Start date of imAE episode + 1
- Time to resolution of Grade 3 or 4: End date of imAE episode that had CTCAE Grade 3 or 4 – First date imAE episode had severity of grade 3 or higher + 1

If an imAE does not resolve, then the time to resolution will be censored at earliest date of DCO, death date, or last dose date + 90 days. Patients who die prior to resolution of the imAE will be censored at the date of death.

Adjudication and statistical analysis for the imAEs will be performed by AstraZeneca. The results will be incorporated into and discussed in the CSR.

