8.3.1 Method of detecting adverse events and serious adverse events

Care will be taken not to introduce bias when detecting AEs and/or SAEs. Open-ended and non-leading verbal questioning of the patient is the preferred method to inquire about AE occurrences.

8.3.2 Time period and frequency for collecting adverse event and serious adverse event information

AEs and SAEs will be collected from time of signature of informed consent throughout the treatment period and including the follow-up period (90 days after the last dose of IP). If an event that starts post the defined safety follow-up period noted above is considered to be due to a late-onset toxicity to study drug then it should be reported as an AE or SAE, as applicable.

All SAEs will be recorded and reported to the Sponsor or designee within 24 hours, as indicated in [Appendix B](#). The Investigator will submit any updated SAE data to the Sponsor within 24 hours of the data being available.

Investigators are not obligated to actively seek AE or SAE in former study patients. However, if the Investigator learns of any SAE, including a death, at any time after a patient's last visit and he/she considers the event to be reasonably related to the study drug or study participation, the Investigator may notify the Sponsor.

The method of recording, evaluating, and assessing causality of AE and SAE and the procedures for completing and transmitting SAE reports are described in [Appendix B](#).

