8.3.4 Adverse event data collection

The following variables will be collected for each AE:

- AE (verbatim)
- The date when the AE started and stopped
- The maximum CTCAE Grade reported

- Changes in CTCAE Grade (report only the maximum CTCAE Grade for the calendar day)
- Whether the AE is serious or not
- Investigator causality rating against the IPs (yes or no)
- Action taken with regard to IPs
- Administration of treatment for the AE
- Outcome

In addition, the following variables will be collected for SAEs:

- Date the AE met criteria for SAE
- Date the Investigator became aware of the SAE
- Seriousness criteria fulfilled
- Date of hospitalisation
- Date of discharge
- Probable cause of death
- Date of death
- Whether an autopsy was performed
- Causality assessment in relation to study procedure(s)
- Causality assessment in relation to other medication, as explained in Section 8.3.5
- Description of the SAE

The grading scales found in the revised NCI CTCAE version 4.03 will be utilised for all events with an assigned CTCAE grading. For those events without assigned CTCAE grades, the recommendation in the CTCAE criteria that converts mild, moderate, and severe events into CTCAE grades should be used. A copy of the CTCAE version 4.03 can be downloaded from the Cancer Therapy Evaluation Program website (<http://ctep.cancer.gov>).

It is important to distinguish between serious and severe AEs. Severity is a measure of intensity, whereas seriousness is defined by the criteria in [Appendix B, B 2](#). An AE of severe intensity need not necessarily be considered serious. For example, nausea that persists for several hours may be considered severe nausea, but not an SAE unless it meets the criteria shown in [Appendix B, B 2](#). On the other hand, a stroke that results in only a limited degree of disability may be considered a mild stroke, but it would be an SAE if it satisfies the criteria shown in [Appendix B, B 2](#).

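### The imAE onset formula in SAP 3.2.3.3 has no rule for an event that starts before first dose and worsens on drug, so it returns an onset of zero or below

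*SAP*

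**What the plan says.** SAP 3.2.3.3 gives four imAE timing formulas. Any-grade onset is "Time to first onset of imAE: Start date of first imAE episode – First dose date + 1". Any-grade resolution runs from the episode's start date to its end date, plus 1. Grade 3/4 onset uses the "First date of imAE episode that had CTCAE Grade 3 or 4", less the first dose date, plus 1. Grade 3/4 resolution is the end date of the episode minus "First date imAE episode had severity of grade 3 or higher + 1".

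SAP 3.2.3 includes among treatment-emergent events those "which start prior to the first dose of durvalumab but worsen following the first dose of durvalumab". It uses the date of worsening in its time limit: "where the start date/date of worsening is also no later than 90 days after the last dose of durvalumab". SAP 4.5.1.1 refers to treatment-emergent imAEs, so this definition applies to imAEs too.

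Start dates before first dose can exist, because under Protocol 8.3.2 "AEs and SAEs will be collected from time of signature of informed consent throughout the treatment period". SAP 4.1.3 moves a start date up to the first dose date only when the date was incomplete and its imputation falls before first dose. SAP 4.5.1.1 merges imAEs with different preferred terms in one AESI category when the gap is 3 days or less, and takes onset from the first preferred term.

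**The concern.** The SAP recognises the date of worsening when it decides whether an event is treatment-emergent, then does not carry that date into the onset formula. For an event that began before dosing, the formula gives an onset earlier than the first infusion, which cannot be a time from treatment to toxicity. The any-grade duration of the same event then includes days when the patient had received no drug.

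The setting makes the case credible. Every patient had 54 to 66 Gy of thoracic radiation completed within 42 days before first dose (Protocol 5.1), and exclusion criterion 11 bars unresolved toxicity only from Grade 2 upwards, with exceptions. Protocol 4.2.1 itself raises the possibility that radiotherapy makes anti-PD-L1 pneumonitis more likely. A mild lung event first recorded in screening that worsens on durvalumab and is called immune-mediated is the kind of record the formula mishandles.

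At stake is the accuracy of the descriptive imAE onset and resolution summaries by AESI category.

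**Working it through.** The plan prints no figure that depends on these formulas, so there is nothing to reproduce. The check applies the SAP 3.2.3.3 formulas to assumed dates, counted in days relative to first dose (first dose = 0).

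**Step 1. Any-grade onset = start - first dose + 1.**

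| Episode starts | Calculation | Onset |
|---|---|---|
| 20 days before first dose | -20 + 1 | -19 |
| 10 days before | -10 + 1 | -9 |
| 2 days before | -2 + 1 | -1 |
| 1 day before | -1 + 1 | 0 |
| Day of first dose | 0 + 1 | 1 |

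Every start before first dose gives zero or a negative value.

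**Step 2. The reset in SAP 4.1.3.** If the day of onset is missing and the imputed date falls before first dose, the start date becomes the first dose date and onset is 0 + 1 = Day 1. With the date fully known as 10 days before first dose, no reset applies and onset is Day -9. The more complete record gets the less usable value.

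**Step 3. A full example.** Grade 1 starts 10 days before first dose, worsens 20 days after it, reaches Grade 3 at 60 days and ends at 100 days.

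- Onset by the SAP formula: -10 + 1 = Day -9. From the date of worsening: 20 + 1 = Day 21.
- Any-grade resolution by the SAP formula: 100 - (-10) + 1 = 111 days, of which 10 precede any drug. From the date of worsening: 100 - 20 + 1 = 81 days.

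**Step 4. The Grade 3/4 onset bullet.** Take an episode wholly on drug: Grade 1 at 20 days after first dose, Grade 3 at 60, ended at 100 (end day 100 + 1 = 101). The resolution bullet is clear and gives 100 - 60 + 1 = 41 days.

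- Read as the start of an episode that at some time had Grade 3/4: onset is Day 21, and 21 + 41 - 1 = 61, which is 40 days short of the end day.
- Read as the first date at Grade 3/4: onset is Day 61, and 61 + 41 - 1 = 101, the end day.

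Only the second reading is consistent with the resolution bullet.

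**The case against.** The strongest reply is that few records can reach this formula. The event must begin between consent and first dose (screening is Days -28 to -1), be recorded as an AE, worsen within the same record, and be classed as an imAE. That class requires a link to drug exposure and no other clear cause, and the sponsor adjudicates it; a lung event that began soon after radiation and before any durvalumab will often have another explanation. Screening examination findings go to medical history (SAP 3.2.7), and Protocol Appendix B 1 lets a deterioration of an existing condition count as an AE, so toxicity present before consent may enter as a new AE with a start date after dosing. All of this stands and narrows the group. None of it excludes an event aggravated by the drug, and no rule says what its onset date is.

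A reader might also infer that the SAP dates Grade 3/4 onset to the earlier low-grade start. The documents do not support that as a statement of the rule. The any-grade bullets speak of a start date; the Grade 3/4 bullets change to a first date, and the resolution bullet counts from when Grade 3 was reached. The phrase is loose, and for merged episodes the first-preferred-term rule has no separate Grade 3/4 provision, so a programmer could take the early date. That is an ambiguity to close. The merging rule itself is an explicit choice and is not faulted here.

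**Conclusion.** The gap is real and minor. For a treatment-emergent imAE that began before first dose, SAP 3.2.3.3 gives an onset of zero or below and an any-grade resolution time that includes days before dosing. This rests on two assumptions that the documents allow but do not assert: that such an event can be classed as an imAE, and that its worsening is kept within the same AE record.

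The number of patients is unknown and probably small. For scale, if the any-grade imAE rate that Protocol 2.3.2.1 reports for PACIFIC (24.2%) applied to 150 patients, about 0.242 x 150 = 36 patients would have an imAE; the documents do not say what share would have started before dosing. Only secondary descriptive imAE timing outputs are affected. The primary endpoint, incidence of Grade 3 and 4 treatment-related AEs to Day 183, does not use these formulas.

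Two further inferences are tempting and go beyond the documents. One is that affected patients would drop out of the onset analysis because the software rejects negative times. SAP 4.1.1 names the SAS LIFETEST procedure only for confidence-interval methods, and SAP 4.5.1.1 mentions Kaplan-Meier for imAEs only for time to resolution. The other is that the error undermines a study claim that severe toxicity falls within 6 months. Protocol 4.2.1 uses imAE timing from PACIFIC and the literature as design rationale and makes no such claim. Nor do the documents allow the shift in any median onset to be estimated.

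**What to change.** In SAP 3.2.3.3, add that for a treatment-emergent imAE that began before first dose, the onset date is the date of its first grade increase on or after first dose, and that the same date is the origin for any-grade time to resolution.

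As a wording clarification, restate Grade 3/4 onset as the first date on or after first dose at which the episode, merged or not, reached Grade 3 or higher, minus first dose date, plus 1. Use that same date as the origin in the Grade 3/4 resolution formula.

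The cost is two sentences in the SAP and slightly more programming. Protocol 8.3.4 already has grade changes recorded by calendar day, so no new data are needed.

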## 4. ANALYSIS METHODS

### 4.1 General Principles

#### 4.1.1 General Statistical Considerations

The following general statistical considerations will be applied for the analyses and presentation of the data. In case of any specific deviations, methods will be specifically noted on the relevant output.

- All data, demography, baseline characteristics, safety, efficacy and biomarkers, will be summarized using descriptive statistics, as appropriate for the type of data, for the SAF. In addition, all efficacy and safety data and some selected relevant data (eg, patient disposition, demography and baseline characteristics) will be summarised separately for the WHO/ECOG PS 0 to 1 and 2 groups.
- Continuous variables will be summarized by the number of observations (n), mean,

standard deviation, median, minimum, and maximum.

- For the continuous data, the summary statistics will be displayed with the following accuracy (number of dps):
  - The minimum and maximum with same accuracy as the raw data.
  - The mean and median will be rounded to 1 additional dp more than the number of dps in the raw data.
  - The standard deviation will be rounded to 2 additional dps more than the number of dps in the raw data.
  - If the number of observation is 1, the SD will not be derived.
- Categorical variables will be summarized by frequency counts and percentages for each category and percentages will be rounded to one dp.
- As a default, percentages will be calculated using the number of patients who have non-missing data as the denominator. Therefore, percentages for missing data will not be presented in the results. If the denominator is different from this default, it will be explained in a footnote to the output.
- SAS® version 9.3 or higher will be used for all analyses.
- Exact CIs for proportions will be calculated using the Clopper-Pearson method.
- For percentiles of survival times based on the Kaplan-Meier method (eg, median survival), CIs will be calculated using the default method available in the SAS LIFETEST procedure (ie, the Klein and Moeschberger extension of the Brookmeyer-Crowley method).
- For point-estimates of survival based on the Kaplan-Meier method (eg, for PFS12), CIs will be calculated using the default method available in the SAS LIFETEST procedure (ie, using Greenwood's estimate of standard error and a log-log transformation).
- The data will be included in summaries/analyses using the following criteria:

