#### **4.5.1.1 Adverse Events of Special Interest and Immune-Mediated Adverse Events**

The following summaries of AESIs will be presented by AESI category and PT:

- All AESIs / TRAEs of special interest
- All serious AESIs
- All AESIs by maximum CTCAE Grade
- All AESIs by outcome
- All AESIs leading to treatment interruption
- All AESIs leading to treatment discontinuation
- All AESIs / TRAEs of special interest with fatal outcome
- All AESIs which required treatment
- All AESIs which required treatment with systemic steroids, and high dose steroids
- All AESIs which required treatment with immunosuppressants
- All AESIs which required treatment with endocrine therapy

Overall summaries will present the numbers and percentages of patients with at least one immune-mediated AE (imAE) by the following categories:

- AEs / TRAEs,
- AEs / TRAEs of CTCAE Grade 3 or Grade 4
- SAEs / Serious TRAEs
- AEs / TRAEs with outcome of death
- AEs which required treatment
- AEs which required treatment with systemic steroids, and high dose steroids
- AEs which required treatment with immunosuppressants
- AEs which required treatment with endocrine therapy
- AEs leading to treatment discontinuation
- AEs by outcome

Using the same categories above similar summaries will be presented by preferred term, and by SOC and PT.

Time to event analyses for immune-mediated AE (imAE) will be performed by AESI categories, for:

- Time to first onset of imAE
- Time to first onset of imAE of Grade 3 or 4
- Time to resolution of imAE
- Time to resolution of Grade 3 or 4

For patients with imAEs having multiple PTs within an AESI category the AEs will be collapsed to one event if the difference between end date of an imAE and subsequent start date of the next imAE is  $\leq 3$  days. The time to onset will be based upon the first PT, whereas time to resolution used for KM analysis will be based on time of the worst imAE episode from that given patient.

At the AESI grouped term level for time to resolution outputs the worst imAE is defined in the order of the following:

- imAE with worst (highest) grade first
- For more than one imAE with the same highest grade take imAE which did not resolve before imAE which did resolve
- If multiple imAE and all resolved take imAE with longest duration

Summaries for imAEs and related data will be presented by imAE category and PT:

- At least one imAE
- At least one serious imAE
- At least one imAE by outcome

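### Time to resolution of immune-mediated AEs: censoring deaths in a Kaplan-Meier analysis overstates the probability of resolution when a patient dies unresolved and others resolve later

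*SAP*

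**What the plan says.** SAP 3.2.3.3 defines time to resolution for all imAEs and for Grade 3 or 4. For an imAE that does not resolve, "time to resolution will be censored at earliest date of DCO, death date, or last dose date + 90 days". The next sentence adds: "Patients who die prior to resolution of the imAE will be censored at the date of death".

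SAP 4.5.1.1 supplies the estimator and the unit. "Time to event analyses for immune-mediated AE (imAE) will be performed by AESI categories", and "time to resolution used for KM analysis will be based on time of the worst imAE episode from that given patient". The worst episode is chosen in order: "imAE with worst (highest) grade first"; then "For more than one imAE with the same highest grade take imAE which did not resolve before imAE which did resolve"; then the longest. SAP 3.2.3 lists "Grade 5: Death related to AE" as the top grade.

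SAP 4.1.1 covers survival-type curves only through Kaplan-Meier: "For percentiles of survival times based on the Kaplan-Meier method (eg, median survival), CIs will be calculated using the default method". No cumulative-incidence or competing-risk method appears in the SAP.

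SAP 4.5.1.1 also plans separate counts of imAEs by outcome and of imAEs with a fatal outcome.

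**The concern.** Death rules out resolution, and for a fatal imAE it is the outcome of the event itself. Kaplan-Meier with death censored passes the dead patient's weight to those still unresolved, as though the same later chance of resolving applied. The worst-episode rule brings these cases into the curve. A fatal episode has the highest grade, and even if it were carried at Grade 4 the second rule would place it ahead of a resolved episode of equal grade.

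Reversibility of immune-mediated toxicity is a planned question here. Protocol 9.4 item 6(c) includes the time from AESI onset to resolution among the possible outcome measures, and Protocol 4.2.1 gives the outcome of treated toxicities as part of the safety rationale. The error from censoring deaths runs in one direction only: it makes toxicity look more reversible.

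**Working it through.** The documents give no resolution probability and no count of imAE deaths, so there is no plan figure to reproduce. The check compares the planned estimator with the one that treats death as a competing event.

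**1. Direction.** At each resolution time u, let d be the number resolving and r the number at risk. 1-KM rises by K(u-) × d/r, where K is the Kaplan-Meier curve with deaths censored. The Aalen-Johansen curve rises by S(u-) × d/r, where S is the probability of being neither resolved nor dead. S equals K until the first death and is smaller afterwards. So 1-KM is never below the cumulative incidence, and it is above it once a resolution follows a death.

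**2. Ten patients (invented data).** Six resolve on days 10, 20, 30, 40, 60 and 80; two die unresolved on days 25 and 50; two are ongoing at day 120.
- 1-KM = 1 - (9/10 × 8/9 × 6/7 × 5/6 × 3/4 × 2/3) = 71.4%.
- Aalen-Johansen = 6 × 1/10 = 60.0%, which is the true 6 of 10.
- Both curves first reach 50% on day 60, so the median does not move.
- With the two deaths replaced by living patients ongoing at day 120, Kaplan-Meier also gives 60.0%.

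**3. Expected curve sizes.** Protocol 2.3.2.1 quotes PACIFIC imAE rates of 24.2% overall and 3.4% for Grade 3 or 4. These are used only for scale.
- All imAEs: 0.242 × 120 = 29 and 0.242 × 150 = 36 patients.
- PS 2 cohort: 0.242 × 30 = 7 patients.
- Grade 3 or 4: 0.034 × 120 = 4 and 0.034 × 150 = 5 patients.

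These numbers are then divided by AESI category.

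**4. Five Grade 3 or 4 patients (invented data).** One dies on day 20; three resolve on days 30, 45 and 60; one is ongoing at day 90.
- 1-KM = 1 - (3/4 × 2/3 × 1/2) = 75%, first reaching 50% on day 45.
- Aalen-Johansen = 3/5 = 60%, first reaching 50% on day 60.
- If all four survivors resolve, 1-KM is 100% with one patient dead; Aalen-Johansen is 4/5 = 80%.

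**5. Simulation.** There are 29 imAE patients per run and 1,500 runs per scenario. All of the following are assumptions: exponential times with median 60 days to resolution and 30 days to death; independent censoring uniform over 90 to 720 days; a share f dying unresolved; a share g alive and never resolving. True resolution by day 180 is (1 - f - g) × (1 - 2^(-180/60)) = (1 - f - g) × 0.875.

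| f | g | 1-KM | Aalen-Johansen | True | Gap, 1-KM less Aalen-Johansen (points) |
|---|---|---|---|---|---|
| 0% | 30% | 61.5% | 61.5% | 61.2% | 0 |
| 3% | 30% | 60.3% | 58.9% | 58.6% | 1.4 |
| 7% | 30% | 58.3% | 55.2% | 55.1% | 3.1 |
| 10% | 30% | 56.8% | 52.5% | 52.5% | 4.3 |
| 20% | 30% | 51.8% | 44.0% | 43.8% | 7.8 |
| 10% | 0% | 86.3% | 78.5% | 78.8% | 7.8 |

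**6. The cut-off at last dose plus 90 days.** The SAP applies it to imAEs that do not resolve and does not say how a resolution recorded after that date is handled. A variant with no deaths and 30% never resolving cut only the non-resolvers, at 30 to 180 days, and counted every resolution. It gave 73.6% against a true 61.2%, under either estimator. The text permits this reading but does not state it.

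**7. The two censoring sentences.** For a death after last dose plus 90 days, the first gives last dose plus 90 days and the second gives the date of death.

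**The case against.** The strongest reply is that little depends on this curve. The study tests no hypothesis (Protocol 9.1), the primary endpoint is untouched, and no decision rule uses time to resolution. The SAP does not say that 1-KM will be reported as the proportion resolved. Fatal and outcome counts are tabulated directly, so fatal imAEs are not hidden. The worst-episode rules also choose the least favourable episode, which works against the drug. All of this is correct and limits the consequence. It does not make the curve or its quantiles right, and a Kaplan-Meier curve near 100% would sit beside a table showing a death.

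Three stronger readings are tempting and not supported:

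- A reader might infer that every unresolved imAE inflates the result. An unresolved event in a living patient is ordinary right-censoring. With 30% never resolving and no deaths, the simulation gave 61.5% against a true 61.2%. Overstatement from that source would need an informative or one-sided cut-off, which the text does not establish.
- A reader might infer that the median is always too short. It can be, as in the five-patient example, but in the ten-patient example it is unchanged.
- A reader might put a firm size on the bias, for instance in standard errors of one pooled curve or at 12 months. The curves are drawn by AESI category, and censoring at last dose plus 90 days leaves early stoppers without 12 months of follow-up. The documents give no imAE fatality share or resolution rate for this setting.

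**Conclusion.** The point holds for death before resolution and for nothing wider. As planned, 1-KM overstates the cumulative probability of resolution whenever a patient dies unresolved and others resolve later, and the median may be too short. There is no bias if nobody dies unresolved.

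The size rests on assumption: about 1 to 8 percentage points at day 180 for fatal shares of 3% to 20%, with the timing assumed above. In a category or Grade 3 or 4 curve of four or five patients, one death can move the estimate by more, as the 75% against 60% example shows. The effect is confined to a descriptive secondary safety output. It is worth correcting because the bias has one direction and the correction needs no new data.

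**What to change.** In SAP 3.2.3.3 and 4.5.1.1:

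1. Estimate the cumulative incidence of resolution by Aalen-Johansen with death from any cause as a competing event, for all imAEs and for Grade 3 or 4.
2. Censor only at the earlier of DCO and last dose plus 90 days, and apply that cut-off alike to resolutions, deaths and unresolved events. This also removes the conflict between the two censoring sentences and the one-sided reading.
3. Take the median from that curve, and report it as not reached where the curve stays below 50%.
4. Add the matching confidence-interval method to SAP 4.1.1, which currently covers Kaplan-Meier quantities only.

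The cost is SAP wording, minor reprogramming of the imAE outputs, and slightly less favourable resolution figures if any patient dies unresolved.
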